Blood Sampling††	BL1		BL2	BL3	BL4	BL5			BL6 (all subjects)	BL10 (subgroup b only)			BL9 or BL13‡‡	
30-min observation period	√		√		√				subgroup a: V07 Y1 subgroup b: V07 Y2		√	√	√	
Injection site reactions & systemic events§§	√	√	√	√	√	√								
Diary Card (DC): Provided:	DC1		DC2		DC3				DC4 or DC4 Group b or MA2	DC5				
Checked and/or collected:		DC1		DC2		DC3			***	DC4 Group b ***	DC4/DC5	DC4/DC5	DC4/DC5	
Memory Aid (MA): Provided:						MA1								
Checked:							MA1		MA1				MA2	MA2
Termination Record													√	
SAEs and Serious AESIs†††	To be reported throughout the study period													
THE FOLLOWING ADDITIONAL PROCEDURES APPLY ONLY TO THE AIT SUBSET														
Additional neutralizing Ab											BL7 or BL11‡‡	BL8 or BL12‡‡		
Affinity maturation and specificity assays	BL1					BL5			BL6‡‡	BL10‡‡	BL7 or BL11‡‡ ‡‡‡	BL8 or BL12‡‡ ‡‡‡	BL9 or BL13‡‡	
CMI	BL1								BL6‡‡	BL10‡‡	BL7 or BL11‡‡	BL8 or BL12‡‡	BL9 or BL13‡‡	

STAGE I							STAGE II*							
Visit Number (V)	V01	V02	V03	V04	V05	V06	6M FU (PC7)†	V06_Inf	V07 (Y1)	V07 (Y2)	V08 (Y1/Y2) (AIT only)	V09 (Y1/Y2) (AIT only)	V10 (Y1/Y2)	6M FU (PC)‡
Trial timelines (Days/Months)	V01	V01+ 28d	V01+ 180d	V03+ 28d	V01+ 365d	V05+ 28d	last inj + 6M		V05+ 12M	V05+ 24M	V07+ 7d	V07+ 14d	V07+ 28d	V07+ 6M
Time Windows (Days)		+14d	±20d	+14d	±20d	+14d	+20d		+60	+60	+3d	+7d	+14d (+7d for AIT)	+20d

NAb: neutralizing antibodies; CMI: cellular mediated immune response; Aff: affinity; AIT: Additional Immunological Testing subset.

- * As described in the synopsis, dengue seronegative subjects at baseline will attend Y1 V07 and have the possibility to provide BL6 once having consented to continue in the trial. After the Y1 V07, they will no longer have to come back to the site.
- † See [Table of procedures \(Phone Contacts\)](#). Subjects having prematurely terminated the trial will be contacted by phone for the 6-month safety follow-up.
- ‡ See [Table of procedures \(Phone Contacts\)](#). Subjects eligible to booster injection will be contacted by phone for the post-booster injection 6-month safety follow-up (PC12 for subjects from subgroup a and PC15 for subjects from subgroup b). Subjects non-eligible to booster injection will be contacted by phone as part of the safety follow-up.
- § Axillary temperature will be obtained for vaccination visits; also, note that febrile illness on the day of vaccination is a temporary contraindication.

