Remind subject / parent / legal acceptable representative to notify the site in case of an SAE	√	√	√	√	√	√	√	√	√	√	√	√	√	√	√
Review MA§ subgroup a subgroup b					MA1	MA1	MA1	MA1	MA1	DC4 or MA2	DC4	DC4			
					MA1	MA1	MA1	MA1	MA1	DC4 Group b or MA2	DC4 Group b	DC4 Group b	DC4 Group b	DC4 Group b	MA2

* At PC7, all subjects will receive a post-Injection 3 safety follow-up phone call. At PC12, subgroup a subjects will receive the post-booster injection safety follow-up phone call, while subjects in subgroup b will receive a standard phone call from the study center.

† PC13 to P15 will be made only for subgroup b subjects. PC15 will be subgroup b post-booster injection safety follow-up phone call

‡ If an SAE occurred, instructions in [Section 10](#) for reporting are to be followed

§ Review information entered into MA by interviewing subject / subject's parent(s) / legally acceptable representatives and request information concerning any medical event serious or not, that may have occurred since Visit 6

List of Abbreviations

Ab	antibody
ASC	antibody secreting cells
AE	adverse event
AESI	adverse event of special interest
AF	assent form
AIT	additional immunological tests
ALT	alanine aminotransferase
ANCOVA	analysis of covariance
AR	adverse reaction
AST	aspartate aminotransferase
BL	blood sample
BSA	bovine serum albumin
CCID ₅₀	cell-culture infectious dose 50%
CDM	Clinical Data Management
CI	confidence interval
CMI	cell-mediated immunity
CQA	Clinical Quality Assessment
CRA	Clinical Research Associate
CRF; eCRF	case report form; electronic case report form
CRO	contract research organization
CTA	clinical trial agreement
CTL	Clinical Team Leader
CYD	chimeric yellow fever/dengue
D	day
DC	diary card
DF	dengue fever
DHF	dengue hemorrhagic fever
EDC	electronic data capture
ELISA	enzyme-linked immunosorbent assay
ELISPOT	enzyme-linked immunospot
FAS	full analysis set
FDA	Food and Drug Administration
FUP	follow-up
FV	flavivirus
FVFS	first visit, first subject

FVLS	first visit, last subject
GCI	Global Clinical Immunology
GCP	Good Clinical Practice
GMR	geometric mean ratio
GMT	geometric mean titer
GMTR	geometric mean titer ratio
GPV	Global PharmacoVigilance
IATA	International Air Transport Association
ICF	informed consent form
ICH	International Council for Harmonisation of Technical Requirements for Pharmaceuticals for Human Use
IDMC	Independent Data Monitoring Committee
IEC	Independent Ethics Committee
Ig	immunoglobulin

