Each STAGE II subject will provide blood samples for assessing neutralizing Ab titers against each of the 4 parental dengue virus strains. The first blood sample will be collected in all subjects approximately 1 year post last primary series injection. This blood sample will be used to assess both the Ab persistence at 1 year in all subjects and the pre-booster Ab levels in subgroup a. Subjects receiving the booster injection will provide additional blood samples. Subjects from subgroup a will provide a second blood sample 28 days after receiving the booster injection. Subjects from subgroup b will provide blood samples immediately before and 28 days after receiving the booster injection.

After a dengue seronegative subject consented to continue in the study, the blood sample collected 1 year after the last primary series injection will be the last clinical procedure required from her/him. After this blood sample, a dengue seronegative subject will no longer be asked to come to the study site. However, the telephone contacts already planned in the study will be maintained as a safety follow-up.

STAGE I and STAGE II

Safety Data Collection

During both STAGE I and STAGE II, reactogenicity data will be collected in all subjects after any injection: immediate adverse events (AEs) observed to occur within 30 min post-injection will be collected; solicited injection site reactions will be collected for Days 0–7; solicited systemic reactions will be collected for Days 0–14; and unsolicited non-serious events will be collected for Days 0–28.

In addition, hospitalized suspected dengue cases occurring at any time in the trial will be documented. Hospitalized suspected dengue disease is defined as an acute febrile illness with a diagnosis of dengue requiring hospitalization (with bed attribution).

Serious and non-serious AESIs will be collected in defined time windows according to the type of AESI. SAEs will be reported throughout the study and until 6 months after booster injection in both subgroups.

Additional Immunological Tests (AIT) Subset

In addition to the blood samples described above, samples will also be drawn from 60 subjects from a specific site in Colombia who consent to participate in the AIT subset.

For evaluations of CMI, Ab specificity and affinity maturation, blood samples will be taken from subjects immediately before Injection 1 (specificity, affinity and CMI) and at 28 days following Injection 3 (specificity and affinity) during STAGE I.

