- 4) **For all subjects:** Collect the fifth blood sample (BL5, 5mL) for neutralizing Abs and record the date of collection (see [Section 7.1.1](#) for detailed instructions regarding the handling of blood samples); the volume used for specificity and affinity maturation testing in the AIT subset will also be used from this aliquot as applicable.
- 5) Give the parent / legally acceptable representative Memory Aid 1 (MA1)
- 6) Remind the parent / legally acceptable representative to have the MA1 with them at the 6 month follow-up telephone contact
- 7) Remind the subject / subject's parent(s) / legally acceptable representative(s) to call the study center if a serious medical event occurs
- 8) Arrange an appointment for Visit 7 (12 months r 24 months [\pm 20-day window] after Visit 5)
- 9) Complete the source documents and relevant eCRF pages for this visit

Telephone Calls: **PC5** (V01 + 14 months [+8-day window]); **PC6** (V01 + 16 months [+8-day window]); **PC7** (V01 + 18 months [+20-day window]); **PC8** (V01 + 20 months [+8-day window]); **PC9** (V01 + 22 months [+8-day window]); **PC10** (V05 + 14 months [+8-day window]), subjects from both subgroups; **PC11** (V05 + 16 months [+8-day window]), subjects from both subgroups; **PC12** (V05 + 18 months [+20-day window]), subgroup a subjects 6-month FUP contact, subgroup b subjects standard phone call contact; **PC13** (V05 + 20 months [+8-day window]), subgroup b subjects; **PC14** (V05 + 22 months [+8-day window] subgroup b subjects); and **PC15** (V05 + 30 months [+20-day window] subgroup b 6-month FUP contact).

- 1) Same procedures as for PC1 and PC2
- 2) Review the information entered into MA by interviewing the subject / subject's parent (s) / legally acceptable representative(s) and request information concerning any medical event, serious or not, that may have occurred since the previous visit or phone call

Visit 6-Inf (unscheduled visit, between PC7 [6 months after last injection in Stage I] and Visit 7–Year 1 [12 Months After Visit 5]): Information of subject on vaccine safety (subgroup a and b)

This unscheduled visit is to take place as soon as possible between V06 and V07. During this visit, subjects will be informed about the increased risk of hospitalized or severe dengue for subjects not exposed to dengue infection prior to the first injection with the CYD dengue vaccine.

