At the latest, this visit will take place at the same time as Y1 V07. In the event the subjects' baseline dengue serostatus is available at the time of V06-Inf, and the Amendment 1 of the protocol is already approved by ECs/IRBs and Health Authorities, subjects could be asked to confirm their willingness to continue participating in the study during this unscheduled visit. If it is not possible to ask for subjects' consent at V06-Inf, subjects will be asked to confirm their participation in the study at Y1 V07.

STAGE II

For each subject, the blood sample collected before first CYD dengue vaccine injection (ie, at V01 for subjects in Group 1, V03 for subjects in Group 2, and V05 in subject in Group 3) will have been assayed with PRNT to determine dengue serostatus at baseline. Only subjects identified as dengue seropositive will be eligible to receive the booster injection.

The blood sample collected 1 year after the last primary series injection will be the last clinical procedure required from dengue seronegative subjects at baseline. Besides the BL6 at Y1 V07, the clinical procedures described hereafter (including the blood samples in the AIT subset) will be for dengue seropositive subjects alone.

One Year Booster (BL6-BL9) or Two Year Booster (BL6; BL10-BL13)

Visit 7–Year 1 (12 Months [+60-day Window] After Visit 5): Booster Vaccination (subgroup a), Collection of Safety Information (subgroup a and b), and Blood Sample (subgroup a and b)

The Investigator or designated study personnel will:

For all subjects:

- 1) Present the changes brought to the study design to the subject / subject's parent (s) / legally acceptable representative(s) in more detail, answer any of his/her/their questions, and ensure that he/she/they has/have been informed of all aspects that are relevant to their decision to continue participating in the study
- 2) Have the subject and / or the subject's parent (s) / legally acceptable representative(s), date and sign the new AF and / or ICF version, as applicable
- 3) Review the pages of the MA with the parent / legally acceptable representative
- 4) **For all subjects having provide their consent:** Collect blood sample (BL6, 5 mL) for neutralizing Abs and record the date of collection (see [Section 7.1.1](#) for detailed instructions regarding the handling of blood samples); the volume used for specificity and affinity maturation testing in the AIT subset will also be used from this aliquot as applicable.

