5.1.5 Planned Trial Calendar

The following dates are approximate. The actual dates may differ as, for example, the trial will not start until all the appropriate regulatory and ethical approvals have been obtained.

- Planned trial period - FVFS to LVLS^a: 26 April 2016 to 20 February 2020
- Planned inclusion period - FVFS to FVLS^b: April 2016 to August 2016
- Planned vaccination period: April 2016 to August 2016
- Planned end of trial: February 2020
- Planned date of final clinical study report: July 2020

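### The last post-booster safety call is timed from the booster in one table and from Visit 5 elsewhere, so a subject boosted late can have the final scheduled call well before 6 months

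*Protocol*

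**What the plan says.** **Rule 1, timed from the booster.** In the Protocol's Table of Procedures for Stages I and II, the last column puts the follow-up call at V07 + 6 months with a +20-day window. Footnote ‡ names the call: "post-booster injection 6-month safety follow-up (PC12 for subjects from subgroup a and PC15 for subjects from subgroup b".

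**Rule 2, timed from Visit 5.** Protocol Section 5.1.4 (Telephone Calls) gives PC12 as "V05 + 18 months [+20-day window]), subgroup a subjects 6-month FUP contact" and PC15 as "V05 + 30 months [+20-day window] subgroup b 6-month FUP contact". The Phone Contacts table uses the same V05 + 18 and V05 + 30 month times, but with a window of +8 days for PC12 and +20 days for PC15.

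SAP Table 3.1 reproduces both tables, conflict included.

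**Booster date.** Section 5.1.4 describes the Year 1 booster visit as "12 Months [+60-day Window] After Visit 5): Booster Vaccination (subgroup a", and the Year 2 visit has the same +60 days. Item 8 under Visit 6 in the same section ("Arrange an appointment for Visit 7 (12 months r 24 months") gives ±20 days instead.

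**The commitment.** Section 5.1.3: "SAEs will be reported throughout the study and until 6 months after booster injection in both subgroups". Protocol Section 9.2.2.3.4 and SAP Section 3.2 say the same.

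**What comes afterwards.** Footnote † of the Phone Contacts table: "PC13 to P15 will be made only for subgroup b subjects". PC12 is therefore the last call for subgroup a, and PC15 is the last for subgroup b.

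**The concern.** The two rules agree only when the booster is given on its nominal date. For a late booster that is still inside the permitted window, a site can comply fully with Section 5.1.4 and the Phone Contacts table and still make its final scheduled call before the 6 months are up.

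PC7 has a similar double timing (6 months after the last injection in one table, V01 + 18 months in the other), but PC8 and PC9 follow it. Nothing follows PC12 in subgroup a or PC15 in subgroup b. For a subject boosted at Year 2, PC15 is the only scheduled contact after the 28-day visit.

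Protocol Section 11.1 makes the 6-month interview the means of capturing SAEs for that period. If it happens early, whole-study counts of SAEs and hospitalised dengue rest, for the remaining weeks, on what subjects report unprompted. Amendment 1 was itself prompted by a dengue-severity signal, so this is not a trivial part of the safety record.

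**Working it through.** **Inputs**
- Booster nominally at V05 + 12 or + 24 months, given *d* days late, with *d* from 0 to 60 (Table of Procedures; Section 5.1.4, Visit 7).
- Call under Rule 2 at V05 + 18 or + 30 months, plus *w* days of window: *w* from 0 to 8 for PC12 in the Phone Contacts table; 0 to 20 for PC12 in Section 5.1.4 and for PC15.
- 6 months = 365.25/2 = 182.6 days.

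**Formulas**
- Rule 2: days from booster to call = 182.6 − *d* + *w*.
- Rule 1: days from booster to call = 182.6 + *w*, with *w* from 0 to 20, whatever *d* is.

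**The plan's own figure.** With *d* = 0 and *w* = 0, Rule 2 gives 182.6 days. The stated 6 months is reproduced for an on-time booster.

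**Late boosters under Rule 2 (days after booster)**

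| Days late | PC12, +8-day window | PC12 (Section 5.1.4) or PC15, +20-day window |
|---|---|---|
| 0 | 182.6–190.6 | 182.6–202.6 |
| 8 | 174.6–182.6 | 174.6–194.6 |
| 20 | 162.6–170.6 | 162.6–182.6 |
| 30 | 152.6–160.6 | 152.6–172.6 |
| 60 | 122.6–130.6 | 122.6–142.6 |

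**Where the rules become incompatible.** A Rule 2 call reaches 6 months only if *w* ≥ *d*. That is impossible once *d* exceeds 8 (PC12, Phone Contacts table) or 20 (PC12 in Section 5.1.4, and PC15).

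**Largest shortfall.** At *d* = 60 it is 60 days if the call is made on the first permitted day (60/182.6 = 32.9%) and 40 days on the last day of a +20-day window (40/182.6 = 21.9%).

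**Sensitivity to the month convention.** Using calendar months for V05 dates from April to September 2017, the call for a 60-day-late booster opens on day 121–124. It closes on day 129–132 (+8 days) or 141–144 (+20 days). Taking 6 months as 180 days, it opens on day 120.

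**Sensitivity to the booster window.** If the ±20 days of Visit 6 item 8 applied, *d* would be at most 20. The largest shortfall would then be 20/182.6 = 11.0%, and a call at the end of a +20-day window would just reach 6 months.

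**Rule 1 throughout.** Follow-up is 182.6 to 202.6 days, or 6.0 to 6.7 months, for every permitted booster date.

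**The case against.** The intent is not in doubt. The main table, its footnote, Sections 5.1.3 and 9.2.2.3.4, and SAP Section 3.2 all point to 6 months after the booster, and even Section 5.1.4 labels the contact a 6-month follow-up. On that reading V05 + 18 and + 30 months are just nominal dates, and a site working from the main table calls at the right time. Day 123 needs three things together: a booster on the last day of its window, a site following the Visit 5 timing, and a call on the first permitted day.

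The consequence is also limited. No primary objective concerns safety, and the safety analyses are descriptive. SAP Section 4.4.2.3.2 tabulates SAEs within 28 days and over the whole study, with no separate 6-month post-booster period. SAE reporting to 6 months stays mandatory, subjects receive a memory aid at V10, and related SAEs after completion must still be reported (Protocol Section 10.3).

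Most of this stands as a limit on size: the 28-day analysis is untouched, and day 123 is an extreme. It does not remove the conflict. Sites read Section 5.1.4 and the Phone Contacts table to schedule calls, and both give an explicit date and window that can be wrong. The shortfall does not need the extreme case: at 30 days late, every date permitted under the Visit 5 rule is at least 10 days early (182.6 − 172.6). Late Year 1 boosters are plausible, because the window only runs later and re-consent under Amendment 1 could be taken as late as Y1 V07.

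**Conclusion.** The point holds. Two current rules fix the same call from different visits, and within permitted conduct the Visit 5 rule breaks the plan's own 6-month commitment. The shortfall is nil for an on-time booster. It becomes unavoidable under the Visit 5 rule beyond 20 days late (beyond 8 for PC12 under the Phone Contacts table), and it reaches 40 to 60 days, or 22–33%, at 60 days late.

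This assumes the +60-day booster window governs and the site follows the Visit 5 timing. If ±20 days governed, the maximum would be 20 days (11%). The proportion of late boosters is not given, so no average effect can be stated. What is shortened is prompted enquiry about SAEs and hospitalised dengue, not the obligation to report them.

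**What to change.** - In the Phone Contacts table, the telephone text of Section 5.1.4 and SAP Table 3.1, set PC12 for boosted subgroup a subjects and PC15 for boosted subgroup b subjects to V07 + 6 months (+20 days). This also settles the +8 versus +20-day discrepancy for PC12.
- Leave subgroup b's standard PC12 call and the calls to unboosted subjects on the Visit 5 timing.
- Correct the ±20-day Visit 7 window in Section 5.1.4, Visit 6, item 8 to +60 days.
- Optionally, add a SAP listing of days of post-booster follow-up.

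**Cost.** The change is to text only and adds no contact, but some calls move later by up to 60 days, with three consequences:
- *End of trial.* Section 5.1.5 has "Planned end of trial: February 2020", which matches August 2016 enrolment + 12 + 30 months. A subgroup b subject enrolled at the end of August 2016 and boosted 60 days late would be boosted at about the end of October 2019 and reach 6 months at about the end of April 2020. The end date may have to move by up to about 2 months.
- *Stated duration.* That subject would also exceed the 42-month upper limit on participation (Synopsis; Section 5.1.1), which would need a matching edit.
- *Call spacing.* For a subgroup a subject boosted 60 days late, the interval from PC11 to PC12 grows from 2 to about 4 months, because PC11 stays at V05 + 16 months and PC12 moves to about V05 + 20 months.
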